7.6.2 Hyperglycemia

If CGM value is >300 mg/dL for 2 hours or >400 mg/dL at any time, check fingerstick BG and ketone level every 60±15 minutes. If unexplained hyperglycemia, evaluate the integrity of the insulin site, consider changing the site and providing a correction bolus as recommended by the bolus calculator. If insulin is given subcutaneous injection rather than through the DiAs, closed-loop control should be suspended for up to four hours unless directed by a study clinician.

7.7 FCL Equipment Training

- **VISIT 6**
- Participants will receive training on at-home use of the study system, safety protocols, and at-home
- study contacts on the day of discharge. Study equipment training is described in section Chapter
- 608 4:.

7.8 Hotel Session Discharge

- Discharge will occur after breakfast on Day 3. After discharge, participants will proceed to the
- Remote Monitored At-Home Phase of the study.

MiniNET 25-Oct-2024 Page 31 of 60

7.9 Other Issues The participant will be instructed to notify study staff if they experience any issues with the study devices. During the hotel phase, staff will provide hands-on support and troubleshooting training

- devices. During the hotel phase, staff will provide hands-on support and troubleshooting training for any device issues. If subcutaneous insulin is needed, the participant will turn off closed-loop
- mode as instructed by study staff. During the at-home phase, participants will be instructed to
- 617 mode as instructed by study starr. During the at-nome phase, participants will be instructed to contact the staff on-call in the event of subcutaneous insulin need. If insulin is delivered by any
- 618 means other than the study pump, the participant will be instructed to turn off closed-loop mode
- for approximately four hours. This timeframe can be adjusted by the study physician.
- The participant will also be asked to alert the study clinical staff for technical issues with the
- Tandem research pump and/or the DiAs system, including use of the study pump and study CGM
- 622 (open loop mode) during periods of component disconnections or technical difficulties.
- Glucagon will be available at the hotel once the investigational system is in place. All participants
- will confirm that they have rescue glucagon available at home for the at-home phase.

MiniNET 25-Oct-2024 Page 32 of 60

Chapter 8: Remote Monitored At-Home Fully Closed Loop Period

626 **VISIT 7**

625

8.1 At Home Participant Plan

- Upon discharge on day 3 of the hotel period, participants will begin a 7 day/6-night Remote
- Monitored At-Home stage of the study. Participants will continue to wear the FCL research system
- as initiated during the hotel period. Participants will be instructed to eat approximately 3 freely
- chosen meals per day without announcing them to the system. The exception is that on 2 separate
- days participants will 1) announce all food intake (triggering an immediate BPS dose) and 2) use
- 633 their usual insulin-to-carbohydrate ratio for all food ingestion. Participants will be instructed to
- participate in their usual level of physical activity. Participants will complete the study after lunch
- on overall study day 9 (Day 7 of the home portion), at which point they will return to use of their
- usual diabetes care.
- Participants in Group A will complete the study after this 1-week FCL data collection period.
- Participants in Group B will then begin the Usual Care control period for data comparison (see
- 639 section 6.1).

8.2 Remote Monitoring

- All participants will continue to be remote monitored during the At-Home period of the study
- using the connection between DiAs and Diabetes Web Monitoring (DWM) platform at UVA.
- Study staff may review the AID system data on the DWM platform as needed; in addition, at each
- site, a licensed medical provider (MD, PA, NP, RN, CDCES) will receive the following automated
- alerts from the DWM (automated notification system, ANS):
- 646 1. CGM > 300 mg/dL for 1 hour.
- 2. CGM < 70 mg/dL for 20 minutes.
- 648 3. CGM < 55 mg/dL at any point.
- 4. No sensor data for > 1 hour.
- The provider on call will contact study participants (e.g., call, text, or video chat) and/or their
- companion for any of the above CGM alerts which are not resolved within a timely manner.
- Participants will be asked to manage glycemic extremes per the hyper- hypoglycemia safety
- 653 protocol.
- 654 Contact (e.g., phone, text, email, etc.) with the study team will occur as needed. Any relevant
- contacts will be recorded on the CRF and summarized as appropriate (e.g. contact that is not a
- scheduling or supplies issue will not be recorded).

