- 473 GROUP A: Participants will complete one week at home usual care before the use of the
- 474 AIDANET system at the hotel admission.
- 475 **GROUP B**: Participants will complete one week at home usual care after the use of the AIDANET
- 476 system at the hotel admission.

MiniNET_25-Oct-2024 Page 27 of 60

496

497

498

499

500

501

502

503

504

505

Chapter 6: Usual Care Control Period 477 478 6.1 Usual Care Control Period 479 VISIT 3 480 During the usual-care control period, participants will continue to use their personal insulin pump 481 in either manual or automated mode. The mode selected must be capable of downloading the data 482 and sharing it with the study team. Participants using Dexcom CGM will continue to use their 483 personal CGM or the study CGM and will share their CGM download data with the study team at 484 the completion of the Usual Care period. 485 All participants will be provided with a study glucometer to collect blood glucose values during 486 the study. This study team will download this glucometer at the conclusion of the study. 487 Participants will be instructed to follow their normal routine involving diet, exercise, and insulin 488 administration. 489 Any relevant contacts will be recorded on the CRF and summarized as appropriate (e.g. contact 490 that is not a scheduling or supplies issue will not be recorded). 491 6.2 Pre-Hotel Check-In Visit 492 VISIT 4 493 All participants will be contacted by the study team approximately 24-48 hours prior to the hotel 494 admission. The study team will verify the following information: 495

a. Inquire about any changes to the participant's medical history

- b. Study equipment (e.g., CGM) has been initiated. A new CGM sensor will be placed approximately 24-72 hours prior to the hotel session for proper warm-up.
- c. Verify with participant that the goal CGM reading at time of arrival is less than 200 mg/dL; this may require contact with the study physician prior to arrival on the day of the study visit.
- d. Participants will be encouraged to complete the INSPIRE and Technology Acceptance surveys prior to the hotel admission but no later than the initiation of the study equipment at the hotel admission.

Should any concerns regarding medical history, pump information, or unforeseen issues arise, the admission will be cancelled for that participant at the discretion of the investigator.

MiniNET 25-Oct-2024 Page 28 of 60

Chapter 7: Supervised Hotel Fully Closed Loop Period

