7.6 Glycemic Treatment Guidelines

- 573 Hypo- and Hyperglycemia occurring while using the AIDANET system will be managed per the
- 574 following protocol during both the hotel and at-home portions of the trial. Glycemic Treatment
- 575 Guidelines will be available for staff use during the study sessions and will be provided to
- participants for the at-home phase of the study.

MiniNET 25-Oct-2024 Page 30 of 60

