14.3 Outcome Measures

14.3.1 Primary Efficacy Endpoint

- The primary metric for analysis will be change in mean CGM between the second last 7 days week
- of the control Usual-Care period and the one-week Remote Monitored At-Home FCL period.

1154 **14.3.2 Secondary Outcomes**

- Glycemic Metrics will be obtained directly from CGM data and will include the standard metrics
- recommended by the international consensus on CGM including mean CGM, GMI derived from
- mean CGM, time in range 70-180 mg/dL, CGM standard deviation (StDev), CGM coefficient of
- variation (CV), CGM %<54 mg/dL, CGM %<70 mg/dL, CGM %>180 mg/dL, and CGM %>250
- 1159 mg/dL. For the Usual Care period, CGM data will be obtained from either the participant's
- personal CGM or a study provided CGM. Data for the control Usual-Care period will be analyzed
- by last available 7-day period. During the FCL period, CGM data will be obtained directly from
- the study device. As GMI is a linear transformation of mean CGM, this metric will have the same
- effect and will be presented as a primary outcome as well. All other glycemic metrics will be
- 1164 considered secondary outcome measures.
- Device-Use Metrics will include time in automation, total daily insulin dose, and number of
- boluses per day. During the Usual Care period, participants using an insulin pump will have their
- pump uploaded at the end of the period to capture their insulin delivery and bolus data. The FCL
- period, insulin use, and bolus data (if any) will be captured from the experimental device.
- Exercise Challenge Metrics will include the duration of exercise, approximate intensity of exercise
- (low, moderate, or high intensity), the % CGM<70 mg/dL, % CGM<54 mg/dL, and any episodes
- of SH (CGM<70mg/dL for more than 15 minutes with interruption, CGM≥70, of less than 15
- minutes or CHO treatment) during and 2 hours after the exercise challenges.
- 1173 Unannounced Meal Metrics during the supervised house/hotel FLC stage participants will be
- instructed to eat at least 3 meals per day. The time of completion for these meals will be recorded
- by study staff. The % CGM>250 mg/dL for the 4 hours after each meal will be recorded and
- specifically analyzed. Participants will be instructed to freely eat meals during the supervised at-
- home FCL stage but will not be required to record the timing of the meals for unannounced meals.

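### Between-week differences in time in low and high glucose combine the AIDANET algorithm with provider alerts and treatment guidelines that the usual-care week is not described as having

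*Combined protocol and SAP*

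**What the plan says.** For the at-home AIDANET week, section 8.2 states: "All participants will continue to be remote monitored during the At-Home period of the study". The feed runs from DiAs to the site's web-monitoring platform (DWM). The automated alerts to a licensed provider include "CGM > 300 mg/dL for 1 hour", "CGM < 70 mg/dL for 20 minutes" and any reading below 55 mg/dL. If an alert is not resolved promptly, "The provider on call will contact study participants (e.g., call, text, or video chat) and/or their" companion, and participants are asked to follow the safety protocol. That protocol is section 7.6, whose scope reads: "Hypo- and Hyperglycemia occurring while using the AIDANET system will be managed per the" guidelines that follow, in both the hotel and the at-home portions.

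For the Usual Care week, section 6.1 tells participants to keep to their normal routine. Dexcom users wear their "personal CGM or the study CGM and will share their CGM download data with the study team at" the end of that week. Section 6.1 describes no provider alert, no undertaking to call and no treatment protocol.

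Section 14.3.2 lists among the outcomes "variation (CV), CGM %<54 mg/dL, CGM %<70 mg/dL, CGM %>180 mg/dL, and CGM %>250" mg/dL. Section 14.1.1 analyses secondary outcomes like the primary, with FCL status as the fixed effect and HbA1c and gender as covariates, or by paired signed-rank test where the distribution is unsuitable. Section 14.4 assesses the system's ability to avoid glucose below 70 mg/dL. Neither analysis takes account of staff contact.

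**The concern.** Percent time below or above a threshold depends on how often glucose crosses it and on how long each excursion lasts. An outside prompt or a treatment protocol can shorten excursions without changing how often the algorithm allows them. If that help is given in one week only, a smaller percentage in that week need not mean better insulin delivery.

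Aim 1 is to evaluate the safety and efficacy of the smaller code version, and section 14.2 ties the sample size to moving on to a larger outpatient efficacy study. A version that produced as many lows as usual care, or slightly more, could still show less time low. That result would be carried forward as algorithm performance.

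**Working it through.** The plan gives no figure for the effect of monitoring, and its sample size of 6 rests on feasibility, so there is nothing to reproduce. The check compares the two weeks and then illustrates the size.

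**Step 1. The two weeks side by side**

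| | At-home AIDANET week | Usual Care week |
|---|---|---|
| Automated provider alerts | Yes, through DiAs and DWM (8.2) | None described; DiAs is not in use |
| Provider contact | Made for unresolved alerts (8.2) | None prescribed; relevant contacts may be logged (6.1) |
| Treatment protocol | 7.6 guidelines, given to participants | Normal routine (6.1); study meter supplied throughout and advised at guideline-defined lows and highs (4.3) |
| Staff view of CGM | Real-time feed, reviewed as needed (2.5, 8.2) | Shared at the end (6.1); clinical account viewable as needed (4.2.2) |
| Participant's own alerts | Not the point at issue | Dexcom app values and alerts may be used (4.2.2) |

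The weeks differ in automated provider alerts, in the undertaking to contact, and in the treatment guidelines.

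**Step 2. Does the analysis separate these from the algorithm?**

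The 14.1.1 model has no term for contact or rescue. The 14.3.3 rules remove CGM data around occlusions and after communication loss, but not after staff contact. Section 14.1.1 mentions a number of hypoglycemia among the outcomes expected to need the signed-rank test. Neither 14.3.2 nor Table 2 lists or defines that count for the two weeks; the only CGM episode definition in 14.3.2 belongs to the exercise challenge. No count of high-glucose episodes appears.

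**Step 3. Possible size (all rescue inputs assumed)**

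Shift in percentage points = 100 × episodes × minutes saved per episode ÷ minutes in the window. A full week is 7 × 1,440 = 10,080 minutes. The 7-day/6-night home stage runs from after breakfast to after lunch, roughly 6.2 days (assumed), or 6.2 × 1,440 = 8,928 minutes.

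- *Lows.* Five episodes of 40 minutes are 200 minutes, or 200 ÷ 10,080 = 1.98%. Saving 5, 10 or 20 minutes each leaves 175, 150 or 100 minutes, or 1.74%, 1.49% or 0.99%. The number of lows is still five.
- *Highs.* Saving 60 minutes on 1, 3 or 7 episodes lowers time high by 60, 180 or 420 ÷ 10,080 = 0.60, 1.79 or 4.17 points. Over 8,928 minutes the figures are 0.67, 2.02 and 4.70.

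The 20-minute saving on a 40-minute low is an upper bound for calls prompted by the below-70 alert, because that alert fires only after 20 minutes. An earlier end needs the below-55 alert or guideline self-treatment. Only savings beyond what participants achieve in usual care would count as bias.

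**Step 4. What a one-directional push can do with six participants**

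The exact two-sided signed-rank p-value with all six differences in one direction is 2 ÷ 2⁶ = 0.031. If one participant goes the other way, even with the smallest rank, it is 4 ÷ 2⁶ = 0.0625. Rescue that tips one participant's sign could therefore move the result across the conventional 0.05 level (assumed, as the plan states no alpha).

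**Step 5. Direction by outcome**

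Ending lows sooner reduces time below 70 and below 54, and ending highs sooner reduces time above 250. Mean CGM rises when lows are treated and falls when highs are corrected, so its net direction cannot be stated.

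**The case against.** The strongest reply is that this is a safety and feasibility pilot, expressly not powered for efficacy, in which remote monitoring is a reasonable safeguard. No go/no-go rule is tied to these percentages. The primary endpoint in 14.3.1 already has remote monitoring in the name of the AIDANET period. Calls follow only unresolved alerts, the high alert needs an hour above 300, and at-home fingerstick confirmation of lows is optional under 7.6.1. Participants also treat themselves in usual care, so the excess rescue may be small.

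Much of this stands. Monitoring is not the defect, and the size is unknown. But low power does not remove a directional bias, and 14.1.1 and 14.4 state the contrast and the safety reading without mentioning monitoring.

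A reader might infer several stronger points that the documents do not support:

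- *That usual care is unmonitored.* Section 4.2.2 allows app alerts and staff viewing as needed. What is missing is an automated provider alert with an undertaking to contact.
- *That Chapter 14 has no episode count at all.* Section 14.1.1 names one for lows; the gap is its definition and the lack of any count for highs.
- *That the primary outcome is biased towards AIDANET.* Step 5 shows that the direction is indeterminate.
- *That time out of range should be credited to the algorithm only if onset counts agree.* The investigator may change the BPS profile and pump settings during closed loop (4.1.1, 4.1.2), and treating one low can affect later onsets and rebound highs. Onset counts are therefore not free of staff influence, and six participants offer no workable criterion for agreement.

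**Conclusion.** The concern holds for percent time below 70, below 54 and above 250 mg/dL, all secondary outcomes. Their between-week differences estimate the algorithm together with provider alerts, contacts and treatment guidelines. The direction probably favours AIDANET. The size cannot be derived from the documents: under the assumed inputs, time below 70 falls by about 0.25 to 0.99 points and time high by 0.60 to 4.17 points over a full week, and the true excess over usual-care self-treatment could be smaller.

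The conclusion assumes that some alerts or guideline treatments end episodes sooner than participants would have ended them in usual care. It does not extend to mean CGM, and it is no criticism of the monitoring. It calls for a cheap improvement in measurement and description; the design need not change.

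**What to change.** Leave monitoring and treatment as they are.

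1. In 14.3.2 and Table 2, define CGM-derived episode-onset counts per day for both the Usual Care week and the at-home AIDANET week. Make onsets below 70 and above 250 mg/dL the main counts. Treat onsets below 54 and above 300 as supportive, since earlier treatment can prevent them. State the return to range that ends an episode and how CGM gaps are handled. Also count, in each week, the episodes that meet the 8.2 CGM alert criteria. This gives the count mentioned in 14.1.1 a definition and adds one for highs.
2. Correct the sentence on contact recording in 6.1 and 8.2. Its parenthesis says that contacts not concerning scheduling or supplies go unrecorded. This looks inverted, and taken literally it would drop the glycemic calls. Once it is corrected, report alerts, provider-initiated contacts and the actions taken, by period, beside the time-out-of-range results.
3. In Chapter 14, describe the contrast as *AIDANET with remote provider monitoring and treatment guidelines versus usual care without automated provider alerts*. Interpret time out of range alongside the onset counts descriptively.

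The cost is a few derived variables from CGM data already collected in both weeks, a corrected sentence, a short contact table and a slightly less favourable claim. No extra visits or staff are needed.

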8.3 Questionnaires

All participants will complete the INSPIRE and Technology Acceptance survey:

MiniNET 25-Oct-2024 Page 33 of 60

659

660

661 8.4 Post-Study Check-In 662 VISIT 8 663 Approximately 24-48 hours after the hotel session, the study team will contact the participant via 664 phone/email/text/video to: 665 • Ask about any changes to the participant's medical history and medication. Review any hypoglycemic events that are less than 60 mg/dL. 666 667 • Review any hyperglycemic events that are more than 300 mg/dL. • Verify that questions have been answered. The study physician or designee will be 668 669 available for any questions related to insulin adjustments/parameters. 670 The study team may contact the participant for issues related to data collection and equipment 671 issues. 672 **8.5** Early Termination Visit (If Applicable) Participants will be asked to attend the Post-Study Check-In Visit (visit 8) in the event of a 673 withdrawal or early termination. 674 675 8.6 Unscheduled Visits 676 Participants may have unscheduled visits during the study period if required for additional device training or other unanticipated needs per the study investigator discretion. 677

• Prior to initiating the study equipment at the hotel admission

At the conclusion of the one week of At-Home FCL data collection.

MiniNET 25-Oct-2024 Page 34 of 60

678

Chapter 9: Medical Monitor Safety Review

The Medical Monitor will review compiled safety data at the conclusion of the trial. In addition, the Medical Monitor will review all DKA and severe hypoglycemia irrespective of relatedness to study device use, and all serious events (including UADEs) related to study device use at the time of occurrence. The Medical Monitor also will be informed of any Adverse Device Effects (ADE) not meeting criteria for a UADE if the Study PI requests the Medical Monitor review. The Medical Monitor can request modifications to the study protocol or suspension or stoppage of the study if deemed necessary based on the totality of safety data available.

MiniNET_25-Oct-2024 Page 35 of 60

686 Chapter 10: Testing Procedures

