Treatment Groups	Randomized Crossover: Participants will be randomized 1:1 to either conduct the control period before use of the AIDANET system (Group A) or after use of the AIDANET system (Group B).
Participant Duration	Approximately 3 weeks: approximately 1 week of usual care, 3 days/2 nights house/hotel in FCL, and 1 week At Home Remote Monitored FCL.
Protocol Overview/Synopsis	We will enroll up to 12 participants with a plan to complete 6 participants. The study will be performed for about 36 hours at a local hotel/rental. Following the house/hotel session, participants will undergo a 7 day/6-night Remote Monitored At-Home use session. We will also conduct a one-week control period gathering data on glycemic control and insulin administration with the participants usual care therapy. Participants will be randomized 1:1, to either Group A (control period prior to AIDANET use) or Group B (control period after AIDANET use).

MiniNET_25-Oct-2024 Page 6 of 60

TABLE 1. SCHEDULE OF STUDY VISITS AND PROCEDURES

	Screening	Randomization	Usual Care Data Collection	Pre-Hotel Check In	Hotel Admission with FCL	FCL Equipment Training	1-week at-home FCL	Post Study Check-In
Location	CV/R/Ph	CV/R/Ph	Home x 1 week	R/Ph	House/ Hotel	House/ Hotel	Home x 1 week	Home
Visit	1	2	3	4	5	6	7	8
Timeframe (days)	1	2	3-10	11	12-14	12	14-21	22
Informed Consent	X							
Eligibility Assessment	X							
Medical History	X							
HbA1c	X							
Pregnancy Test (if applicable)	X							
Blood Testing: BMP, Liver Functioning, Hematocrit, TSH (if requested by MD)	X							
Physical Exam (H&P within 6 months permitted as substitute)	X							
Vital Signs (including height/weight) (self-reported values permitted)	X				X			

MiniNET_25-Oct-2024 Page 7 of 60

Demographic Data Survey (if eligibility is met)	X							
Randomization		X						
Study Equipment Training						X		
CGM Use			X	X	X	X	X	
Fully Closed Loop (FCL) Use (e.g. AIDANET, DiAs, CGM)					X	Х	X	
Questionnaires					X		X	
Concomitant Medication Review	X				X			
Review diabetes management and AEs			X	X	X	X	X	X

CV = Clinic Visit; R=Remote Visit; Ph=Phone which includes text messages and emails

MiniNET_25-Oct-2024 Page 8 of 60

Table 2. Metric Capture Timeline

	Enrollment	1-Week Usual Care	Hotel FCL	1-Week at- home FCL
Visit	1	3	5	7
Demographic Data	X			
HbA1c	X			
CGM Data				
Mean CGM		X	X	X
GMI		X	X	X
TIR 70-180 mg/dL		X	X	X
CGM StDev		X	X	X
CGM CV		X	X	X
CGM%<54 mg/dL		X	X	X
CGM%<70 mg/dL		X	X	X
CGM%>180 mg/dL		X	X	X

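### Section 8.4 times the Post-Study Check-In (Visit 8) from the hotel session, which puts it early in home closed-loop use; Table 1 puts the same visit at day 22, after home use

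*Combined protocol and SAP*

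**What the plan says.** Section 8.4, headed as Visit 8, sets the timing of the closing contact: "Approximately 24-48 hours after the hotel session, the study team will contact the participant via" one of several remote means. It lists what the contact covers: changes in medical history and medication, hypoglycemic events below 60 mg/dL, hyperglycemic events above 300 mg/dL, and any open questions. Section 8.5 uses the same visit for withdrawal or early termination.

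The end of the hotel session is explicit. Section 7.8 says: "Discharge will occur after breakfast on Day 3. After discharge, participants will proceed to the" at-home phase. Section 8.1 starts a home stage of 7 days and 6 nights at that discharge and ends it after lunch "on overall study day 9 (Day 7 of the home portion), at which point they will return to use of their" usual care.

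Table 1 has a last column, "Post Study Check-In", numbered Visit 8. Its timeframe row gives days 12-14 for the hotel, days 14-21 for home FCL and day 22 for Visit 8. The row "Concomitant Medication Review" is marked at Visits 1 and 5 only, and Medical History at Visit 1 only. The row "Review diabetes management and AEs" is marked at Visit 7 as well as Visit 8.

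**The concern.** One numbered visit has two timings, and they fall on opposite sides of most of the home FCL period. Safety and feasibility are the primary objective, and home use is the longest exposure to the new algorithm version. A closing review held on the second or third home day could not cover what happened afterwards.

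The item most exposed is the question on changes in history and medication. History changes are also asked about at the pre-hotel contact (6.2) and at hotel check-in (7.3), and medication review is marked at Visit 5, but all of these precede home use. After discharge, Visit 8 is the only scheduled place for either question. It also holds the only itemised review of glucose events after discharge.

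Two smaller difficulties follow. A participant who stops on home Day 5 is already past the window in 8.4, so 8.4 and 8.5 cannot both be followed. And because section 15.3 treats any departure from the protocol as a deviation, a contact on either date departs from one of the two rules.

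**Working it through.** The check is calendar arithmetic. It needs no clock times.

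**Inputs**
- Hotel on days 12-14, home FCL on days 14-21, Visit 8 on day 22 (Table 1).
- Discharge on hotel Day 3 (7.8); home Day 1 is the day of discharge (8.1).
- Home FCL ends on overall day 9, which is home Day 7 (8.1).
- Visit 8 at 24-48 hours after the hotel session (8.4).

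**Conversion.** Hotel Day 1 is Table 1 day 12, so Table 1 day = hotel-based day + 11. Hotel Day 3 = 3 + 11 = day 14, which agrees with the end of the hotel stay in Table 1. Home Day k is Table 1 day 13 + k.

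**Can 8.4 reproduce day 22?** Day 14 + 1 to 2 days = days 15-16. It cannot: Table 1's date is 22 - 16 = 6 to 22 - 15 = 7 days later. Days 15-16 are home Days 2-3, inside home FCL. On the count in 8.1, discharge on Day 3 plus 1 to 2 days gives Days 4-5, inside the home stage of Days 3-9. This holds for both groups, because in both the home stage follows the hotel directly.

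**Which anchor does give day 22?** The end of home FCL does. Section 8.1 puts that end at day 9 + 11 = 20, while Table 1 puts it at day 21.

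| End of home FCL | Plus 24-48 hours | Includes day 22? |
|---|---|---|
| Day 20 (8.1) | Days 21-22 | Yes |
| Day 21 (Table 1) | Days 22-23 | Yes |

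The one-day difference between 8.1 and Table 1 therefore does not change the answer.

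**Home days after an 8.4 contact**
- Contact on home Day 2: Days 3-7 remain, 5 of 7 = 71%.
- Contact on home Day 3: Days 4-7 remain, 4 of 7 = 57%.

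**What else covers those days**
- Alerts to a provider (8.2): CGM below 55 mg/dL at any point, below 70 for 20 minutes, or above 300 for 1 hour.
- Device data captured in real time and downloaded at the end of home FCL (2.5).
- Adverse event review marked at Visit 7 (Table 1).
- Medical Monitor review of all DKA and severe hypoglycemia at occurrence (Chapter 9 and 12.10), and of compiled safety data at the end of the trial (Chapter 9).
- Re-contact within 2 weeks for adverse events present at completion or leading to withdrawal (12.6).

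Of the glucose events listed in 8.4, two kinds trigger no alert: readings above 300 for under 1 hour, and readings of 55-59 with under 20 minutes below 70. Both remain in the CGM record. The post-discharge question on history and medication has no other scheduled place.

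**The case against.** The best case for leaving 8.4 alone is that an early contact could have been meant. A call a day or two after supervised use ends is sensible, and the offer of help with insulin settings and equipment fits it. This does not explain the visit's name, its number after Visit 7 or its place in the last column, but it cannot be excluded. Re-anchoring would remove such a contact, so the sponsor should confirm that none was intended. Section 6.2 uses the same window before admission ("All participants will be contacted by the study team approximately 24-48 hours prior to the hotel" admission), which may be where the wording came from; that is conjecture and nothing here depends on it.

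A second objection is that little would be lost. Much of this stands. The routes listed above capture serious events, and a new illness could still come to light in the adverse event review at Visit 7. Glucose events below 60 or above 300 mg/dL are not reportable in themselves unless they meet the criteria in 12.2 or are associated with an adverse device effect. A reader might infer that harms late in the home week would go unrecorded. The documents do not support that.

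A third objection concerns Group B. If the name Post-Study shows that day 22 was intended for Group A, the same reasoning points to a contact after usual care for Group B, whose control week comes last (8.1). The review items, on the other hand, are most useful directly after AIDANET use. A reader might infer one answer or the other, but the documents give none: Table 1 shows only the Group A order.

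**Conclusion.** The two timings conflict, and no section reconciles them. Section 8.4 gives days 15-16 and Table 1 gives day 22, 6-7 days apart. The 8.4 anchor is very probably the error, judging from the visit's name, number and position; the protocol does not say so outright.

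If staff followed 8.4 literally, 4-5 of the 7 home days (57-71%) would come after the contact day. The post-discharge question on history and medication and the itemised glucose review would then miss most of the home exposure. These figures rest on the 7-day home stage in 8.1 and on 8.4 being followed in preference to Table 1. If Table 1 is followed, nothing is lost for Group A.

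A reader might also infer damage to the efficacy comparison. There is none: the primary endpoint is computed from CGM data in the two weeks, and Visit 8 does not enter it. This is a minor point, worth correcting because the rule is operative and the correction is cheap.

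**What to change.** 1. In 8.4, for Group A, time the contact at approximately 24-48 hours after the end of the at-home FCL period, or after early termination. This matches day 22 and makes 8.5 workable.
2. Footnote Table 1 to say that its day numbers follow the Group A order.
3. State explicitly whether Group B's Visit 8 follows home FCL or the later usual-care week. The Group A wording should not be applied to Group B by default, since that would settle the question without a decision.
4. Confirm that no separate contact 24-48 hours after the hotel was intended. If one was, list it as its own contact.

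The cost is one changed line, one footnote, one sentence for Group B and two short sponsor decisions. Visit 8 is already planned, so items 1 to 3 add no visit.
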